1
2
3
Regional Health Command-Central (RHC-C)
Institutional Review Board

**HUMAN SUBJECTS RESEARCH
PROTOCOL APPLICATION – Part B**

4
5
6
7
CLINICAL TRIALS: NCT02674711
4 May 2018

1
2
1. **PROTOCOL TITLE:** The Effect of a Pain Medication Educational Approach before Spinal Surgery on 6-month Post-Operative Use of Opioid Medication: A Randomized Clinical Trial

1
2
3
4
2. **ABSTRACT**

5
6
7
Background: Opioid-based pain medication use and prescription has increased dramatically in the last two decades, leading to high rates of overdose and utilization for patients with chronic non-cancer pain, despite lack of evidence to support its use. Very little research has looked at educational strategies to help address this problem.

8
9
Design: Randomized clinical trial

0
1
2
3
4
Methods: Subjects will be recruited from the pool of patients coming in for the pre-operative appointment prior to spine surgery. Patients that consent and enroll will be randomized to receive either a brief educational video at this appointment or usual care. Patients will be followed after surgery weekly for the first month, and then again at 6 months to determine their self reported opioid medication utilization patterns. Pain medication prescription and healthcare utilization will also be abstracted from the MDR healthcare database.

5
6
7
Summary: The results from this study will help inform and develop best practice for managing patients taking opioid medication for surgical pain.

8
9
3. **OBJECTIVES/SPECIFIC AIMS/RESEARCH QUESTIONS.**

0
1
2
3
4
This study is a continued project in a line of research aimed at improving the quality of spinal pain management. The purpose of this project is to assess the impact of an educational tool that addresses the latest evidence regarding the use of opioid medication in a patient-centric fashion. We will assess the impact this shared-decision making educational tool has on 12 month health care utilization post operatively and the self reported use of narcotic pain medication usage for the 6 months following lumbar spine surgery.

5
6
7
Specific Aim 1: Evaluate the differences in opioid medication use for the 12-month period after surgery in subjects that received the education prior to surgery compared to those that received usual care education.

8
9
Specific Aim 2: Compare the changes in self-reported outcome measures (pain, disability, and sleep) between groups over the 6-month period after surgery.

0
1
2
3
4

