Specific Aim 3: Describe the sociodemographic factors and healthcare utilization in enrolled subjects for the 12 months leading up to a surgical procedure for the lumbar spine. Identify factors that could account for differences in opioid medication, and any potential interaction effect between intervention, opioid use, and clinical outcomes following surgery.

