Pittsburg Sleep Quality Index (PSQI) The Pittsburg Sleep Quality Index (PSQI) is a self-rated questionnaire which assesses sleep quality and disturbances. Clinical properties provide utility in both psychiatric clinical practices and research activities. Seven “component” scores including: subjective sleep quality, sleep latency, sleep duration, habitual sleep efficiency, sleep disturbances, use of sleep medication, and daytime dysfunction are generated from 19 individual items.⁶³ Sleep quality may have a significant role in affecting outcomes of patients with low back pain as several studies have shown correlation between chronic back pain and quality of sleep.^{70, 71}

Fear Avoidance Belief Questionnaire (FABQ): The⁷² will be used to measure patients’ beliefs about how physical activity and work may affect their pain and perceived risk for re-injury. The FABQ contains two subscales; a 7-item work subscale (FABQW), and 4-item physical activity subscale (FABQPA). Test-retest reliability of the FABQ subscales is high,^{72,73} and validity is supported by associations with disability and work loss in patients with acute and chronic LBP.^{74,75} Heightened fear-avoidance beliefs have been shown to be a risk factor for the development of chronic LBP following an acute episode.^{62,76} Other research suggests it may be appropriate for other body regions, specifically evaluating its use in lower extremity injuries within a physical therapy setting.⁷⁷

Healthcare Utilization

Finally, healthcare utilization data will be collected from the MHS Data Repository (MDR) database and will be confirmed via AHLTA. Healthcare utilization data will be used to determine any opioid medication use along with any subsequent medical utilization related to low back or neck pain. In order to collect this information a DUA will be completed between the researcher team and Patient Administration Systems and Biostatistics Activity (PASBA) and the Tricare Management Agency (TMA). Both of these agencies require a signed completed IRB protocol prior to submitting the DUA. However, this should not impact the timing of this study; as the data pull will be completed no sooner than December 2015. This will provide more than enough time to complete the DUA with both agencies and submit the signed DUA to the BAMC IRB prior to performing this analysis. Details for the determining healthcare utilization are outlined below:

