Specific Aim #1 will be evaluated by determining the RR (risk ratio) for opioid medication use during the 1 year following surgery between both groups. Utilization reports will be broken down into the 1st week (expected to be the highest), 1st month, and then from 2 through 1 year. We will also look at all healthcare utilization events between patients associated with lumbar ICD-9 codes (Appendix A) in those randomized to also view the educational video.

Comparison of self-report outcomes between groups at baseline and 6 months will be performed using a linear mixed-effects model, which is flexible in accommodating data assumed to be missing at random (Specific Aim #2). The time points will be baseline, 1 month, and 6 months for the measures collected from the patient (self-report questionnaires). Significance is set at 0.05 and 95% confidence intervals will be reported for all relevant data. Sensitivity analysis will be run adjusting for other demographic and/or prognostic variables (PCS, pain intensity, ESS, etc) that may affect the outcome.

Specific Aim #3 will be determined by comparing the variables between each group and introducing them as covariates into the linear mixed-effects model to see if the adjustment influences the differences between each group.

Point estimates with 95% Confidence Intervals will be reported.

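### The analysis stated for Aim 3 does not match two of its three parts: database opioid use gets only an unadjusted risk ratio, and no interaction term is stated

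*Combined protocol and SAP*

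**What the plan says.** Section 3 gives Aim 3 three parts. The first is descriptive: "Describe the sociodemographic factors and healthcare utilization in enrolled subjects for the 12 months leading up to a surgical procedure". The second and third come in one sentence: "Identify factors that could account for differences in opioid medication, and any potential interaction effect between intervention, opioid use, and clinical outcomes following surgery".

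Section 7.4.3 has one sentence labelled for Aim 3. It first compares the variables between the groups and then proceeds by "introducing them as covariates into the linear mixed-effects model to see if the adjustment influences the differences between each group". That model is introduced just before, for Aim 2: "Comparison of self-report outcomes between groups at baseline and 6 months will be performed using a linear mixed-effects model". Section 3 describes the Aim 2 outcomes as "self-reported outcome measures (pain, disability, and sleep", and the list stops there.

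Opioid use appears in section 7.4.3 under Aim 1, by "determining the RR (risk ratio) for opioid medication use" over the year after surgery, split by period. No covariates and no regression model are named for it. The source is the military healthcare database (MDR): "Healthcare utilization data will be used to determine any opioid medication use" (section 7.3.2). Section 7.4.2 places medication use, including narcotics, inside the primary outcome.

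One further sentence, in the mixed-model paragraph, concerns adjustment: "Sensitivity analysis will be run adjusting for other demographic and/or prognostic variables (PCS, pain intensity, ESS, etc) that may affect the outcome".

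**The concern.** An aim about what drives opioid use needs a model with opioid use as the outcome. An aim about an interaction needs an interaction term. The Aim 3 sentence supplies neither. It directs the reader to a model whose stated outcomes are pain, disability and sleep, and asks whether main-effect covariates shift the arm difference.

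An analyst who followed the plan could describe the sample and adjust the self-report comparisons, but would have no specified route to the other two parts. Any later opioid-factor or interaction result would rest on choices of model, factors and terms that the plan does not fix.

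It would also rest on an undefined variable. Aim 3 does not say whether opioid use in the interaction means use before or after surgery. Use before surgery is a baseline characteristic and can be studied as an effect modifier within the randomised comparison. Use after surgery may itself be changed by the video, so relating it to outcomes is a non-randomised association.

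**Working it through.** The core of the point is textual; the plan states no figure to reproduce.

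**Matching Aim 3 to section 7.4.3**

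| Part of Aim 3 | Analysis stated | Match |
|---|---|---|
| Describe sociodemographics and prior 12-month utilization | Descriptive statistics and group comparisons | Yes |
| Factors behind differences in opioid medication | Variables compared between arms, then entered in the mixed model for self-report outcomes | Weak: a comparison of arms, and a model with another outcome |
| Interaction of intervention, opioid use and clinical outcomes | Covariate adjustment only | No: adding a covariate does not estimate an interaction |

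**What adjusting the opioid risk ratio would gain**

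Inputs: 60 per arm (section 7.4.1), and opioid use R = 1/3. The one third is an assumption borrowed from the Background: it is use at one year in a cited study whose title concerns cervical surgery, whereas this trial expects more lumbar patients. The share of variance explained by pre-operative use, R², is also assumed. The Background says pre-operative use predicts worse outcome, not later opioid use.

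- Unadjusted: SE(log RR) = sqrt(2(1 − R)/(60R)) = sqrt(2 × 0.667/20) = 0.258.
- Adjusted: multiply by sqrt(1 − R²). R² = 0.05 gives 0.252 (2.5% lower), 0.10 gives 0.245 (5.1% lower), 0.20 gives 0.231 (10.6% lower).

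Where use is near-universal, the largest possible R² arises when every prior user uses opioids. With prior-user share p and non-user rate r0 = (R − p)/(1 − p), R² = p(1 − p)(1 − r0)²/(R(1 − R)).

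- R = 0.95: R² = 0.023 (p = 0.3) or 0.053 (p = 0.5), so the SE falls at most 1.1% or 2.7%.
- R = 0.90: R² = 0.048 or 0.111, so the SE falls at most 2.4% or 5.7%.

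**How precise an interaction would be**

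*Opioid model.* Assume 30% to 50% prior users with k = 2 to 3 times the risk of non-users, R = 1/3 overall and no arm effect. Then r0 = R/(1 − p + kp), r1 = k·r0, and the variance of the difference in stratum log RRs is 2(1 − r1)/(60p·r1) + 2(1 − r0)/(60(1 − p)r0).

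- k = 2, p = 0.3: variance 0.244, SE 0.494; upper over lower 95% limit = exp(2 × 1.96 × 0.494) = 6.9.
- k = 3, p = 0.5: variance 0.400, SE 0.632; ratio of limits 11.9.

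The other two corners lie between these. Simulation, which allows for chance variation in cell counts, gave somewhat wider medians of 7.6 to 13.8.

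*Mixed model, as a change-score approximation.* Section 7.4.1 gives an SD of change in OSW of 16 and 85% completion, so 0.85 × 60 = 51 per arm. SE = 16 × sqrt(2/(51p) + 2/(51(1 − p))) = 6.91 (p = 0.3) or 6.34 (p = 0.5). The 95% half-width is 1.96 × SE = 13.6 or 12.4 OSW points, against the plan's minimum important difference of 6.

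Two things move that figure. Adjusting for baseline OSW multiplies it by sqrt((1 + ρ)/2); an assumed baseline-to-follow-up correlation ρ of 0.3 to 0.7 gives about 10.0 to 12.5. Against that, cervical patients complete the NDI instead (section 7.3), so fewer than 51 per arm contribute OSW scores.

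**The case against.** **Aim 3 does have a stated analysis.** This stands in part. A reader might infer that two parts of Aim 3 have none at all, but section 7.4.3 does compare variables between arms, which is a look, if a weak one, at factors behind an arm difference in opioid use. It says little about which factors relate to opioid use, and nothing about interaction.

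**Self-reported opioid use may be a mixed-model outcome.** This is the best counter-argument. The post-operative contacts ask about opioid doses taken (section 7.3), and the assessment schedule lists medication use at baseline, 1 month and 6 months, the mixed model's own time points. It would therefore be too strong to say that opioid use of any kind is certainly never modelled with covariates. But section 7.4.3 ties those time points to questionnaires, section 7.3.2 does not describe medication use among its self-report measures, and the Aim 2 list omits it. The text does not settle the matter. Even on the generous reading, database opioid use has no covariate model and no interaction is named.

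**The sensitivity sentence covers it.** Read as study-wide, it still names no opioid model and no interaction.

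**The wording of Aim 3 is exploratory, and interactions would be uninformative.** Largely fair, and a reason for intervals rather than tests. But the protocol lists Aim 3 beside Aims 1 and 2 without labelling it exploratory, and deleting the interaction clause is an acceptable answer.

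**Randomisation makes adjustment unnecessary.** Correct as to validity. A reader might infer that the crude risk ratio is biased for want of adjustment; the plan gives no ground for that. Randomisation protects the comparison, and the confidence interval already allows for chance imbalance.

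**Conclusion.** The concern holds as a mismatch between an aim and its analysis. The interaction in Aim 3 has no analysis on any reading. The factors question has at best a comparison of variables between arms. Database opioid use, part of the primary outcome, has only an unadjusted risk ratio. The validity of the Aim 1 comparison is not in question.

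The textual finding needs no assumption. The gain from adjustment does: an SE 2.5% to 10.6% lower rests on assumed use of about one third and an assumed R² of 5% to 20%, and it shrinks as use approaches 100%. The interaction widths also depend on assumed prior-use shares and risks. They show only that the trial is not sized for interactions.

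A reader might also infer that all data were in hand at the April 2018 amendment, so that any change is already post hoc. The documents do not show this. Section 7.1.6 says follow-up contact was complete but was still requesting permission to collect the extra utilization data. By the planned dates in section 13.0, enrollment ended in May 2017, so the last 12-month window would close around May 2018. The month 6 to 12 extract may still have been pending, and whether outcomes had been compared by arm is not stated.

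**What to change.** 1. Beside the crude risk ratio for each period, report one from a modified Poisson model (log link, robust standard error), adjusted for pre-operative opioid use from the 12-month database look-back already on the assessment schedule. Write down how pre-operative use is defined.
2. Use that model for the Aim 3 factors question, with a short list of baseline factors named in advance from those collected. Aim 3 itself gives only two broad categories. At one-third use there would be about 120/3 = 40 patients with the outcome, so the list must be short. State also whether self-reported medication use is a mixed-model outcome.
3. State whether opioid use in the interaction is pre- or post-operative. If pre-operative, add arm × pre-operative use to the opioid model and arm × pre-operative use × time (with lower-order terms) to the mixed model, both labelled exploratory and reported with confidence intervals only. If post-operative, report a non-randomised exploratory association. Otherwise delete the interaction clause from Aim 3.
4. Settle this before outcomes are compared by arm and record the date, or label the results post hoc.

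The cost is a paragraph of analysis-plan wording, one clarification from the investigators and a small amount of analysis. No data are needed beyond those already planned, and no further patient contact.

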7.7.1 Certificate of Confidentiality. N/A

8.0 RISKS/BENEFITS ASSESSMENT

8.1 Risks. Risks are unknown, but none are anticipated

There is always a potential risk for loss of confidentiality, but that risk is minimized because we are limiting access to only members of the research team, and have protections in place as we have already outlined, to protect the information.

8.2 Potential Benefits. There are no direct benefits to the patient.

9.0 ADVERSE EVENTS, UNANTICIPATED PROBLEMS, AND DEVIATIONS

9.1 No adverse events are anticipated for this study as it is employing educational material, which is often used in some clinics, but using a novel deployment approach. There is the possibility that the screen from the tablet may be too bright and cause the patient to have to look away, although this would likely be very unlikely and the research assistant can step in and help dim the screen with the appropriate settings. There is also a very minor possibility that the patient may drop the tablet and the screen would shatter, sending sharp glass particles around. However, the tempered glass on the tablets makes this less likely, and the tablets will have cases which should protect them. None of these potential adverse events are serious, and have a very low likelihood of occurring.

In addition, a regular computer can be used to show the video if the tablet becomes a problem.

If an injury does occur, aid will be provided and the patient will be escorted to receive further medical care. The research assistant will help coordinate this with their PCP.

Deviations:

Minor protocol deviations will be reported to the IRB during annual review using the protocol deviation tracking log P53. Major deviations will be reported to the IRB within 48 hours by the primary investigator, in accordance with HRPP policy memo 5.4 on protocol deviations .

9.2 Reporting Unanticipated Problems Involving Risks to Subjects or Others, Serious Adverse Events and Deaths to the RHC-C IRB Office.

All unanticipated problems involving risk to subjects or others, unexpected serious adverse events, and all subject deaths related or possibly related to the study will be reported promptly providing initial notification of the event as quickly as possible after the research team's knowledge of the event, but within five (5) business days of identification by phone, by e-mail, by [contact]) or via letter addressed to IRB Administrator). A complete written report will follow the initial notification within 10 working days.

7 **9.3 Research Monitor.** N/A

8 **10.0 WITHDRAWAL FROM STUDY PARTICIPATION.** Subjects may withdraw at any time by just notifying a member of
9 the investigative team. As the primary outcome measure is healthcare utilization being collected through the MDR
0 database, it will not be affected with patient withdrawal. However, self-report data will not be collected at the 4 and 26-

- 78. Auffinger BM1, Lall RR, Dahdaleh NS, Wong AP, Measuring surgical outcomes in cervical spondylotic myelopathy patients undergoing anterior cervical discectomy and fusion: assessment of minimum clinically important difference. *PLoS One.* 2013 Jun 24;8(6):e67408.

13.0 TIME REQUIRED TO COMPLETE THE RESEARCH (including data analysis).

With an anticipated surgical lumbar surgery load of approximately 20-25 patients per month and a conservative enrollment rate of 50%, we anticipate 1 year for the enrollment period.

- December 2014 – Protocol submitted to BAMC IRB
- April 2015 – Anticipate IRB approval
- March – April 2015 – Study staff training on study procedures
- May 2015 – Subject recruitment/enrollment begins
- May 2017 – Subject recruitment/enrollment end
- November 2017 – Last subject completes 6-month follow-up
- November 2017 – Healthcare utilization data requested from PASBA
- May 2018 – Data analysis and sub-analysis complete
- August 2018 – Publication submitted to appropriate journal

14.0 STUDY CLOSURE PROCEDURES

After all aims have been met, the PI will submit a protocol closure report through IRBNet. Study files will be kept for 6 years and then destroyed.

APPENDICES:

- A. Oswestry Disability Index (OSW):
- B. Numeric Pain Rating Scale (NPRS):
- C. Pain Catastrophizing Scale (PCS):
- D. The Pittsburg Sleep Quality Index (PSQI):
- E. Fear Avoidance Belief Questionnaire (FABQ):
- F. Opioid Risk Tool
